- **6.K.1. Procedures:** Procedures for the monitoring and analysis of data were developed during previous clinical trials conducted at Yale and will be overseen by Drs. [name] and [name].
- 6.K.1.a. To Examine the Efficacy of ZNS (Specific Aim 1), Primary Outcome: We will use *drinks per week* as the primary outcome variable. This is also the primary outcome we are using for veteran ZNS study, and is one that can be readily applied when combining the samples. Recently the NIAAA and FDA Alcohol Clinical Trials Initiative (ACTIVE: a workgroup of experts in the field tasked with optimizing alcoholism clinical trials outcomes and methods) has suggested that for medication development trials and small to medium size trials, continuous outcome variables such as drinks/week or heavy drinking days per week are optimal as opposed to categorical outcomes. We will use a mixed models approach to examine for a statistically significant difference in drinks per week and on continuous secondary outcome variables. The model will include fixed effects for medication group, week, and the interaction between medication and week. We will include pre-treatment drinking behavior (past month HDD) as a covariate and will select the best-fitting variance-covariance structure based on Schwartz-Bayesian Information criterion (BIC). We will incorporate a grace period corresponding to the time it takes to titrate the medication to target dose into the models, and we will focus the primary analysis on the last 8 weeks of treatment at the target dose. All of these outcomes can be obtained from the TLFB data, and from the daily drinking data obtained from the IVR.

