An important initial consideration in considering efficacy will be to identify baseline differences between groups that may have occurred despite randomization. A successful outcome during the treatment trial will be defined in terms of a statistically significant difference on the primary outcome measure: drinks per week, compared during the 8 weeks of active treatment at the target dose, allowing for an 8 week grace period for the medication titration. For all analyses, heavy drinking days will be defined as follows; for men > 4 drinks in a day and for women > 3 drinks in a day. Patients will be followed irrespective of whether they continue to receive medication treatment, so that analysis will include all data available for the 8-week treatment period. All analyses will be **intent-to-treat**. The α will be set at .05 for the primary outcome variable. Between site differences will be explored. We will test interaction effects of GRPS in the regression models for the primary/secondary outcomes (**Exploratory Aim 1**), testing the hypothesis that ZNS's effect on drinking is greater in those with higher GRPS.

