- **6.K. 6. Safety:** Safety will be analyzed using categorical outcomes, defined by the type and severity of adverse effects. Summary measures of adverse events will be developed by organ system from the SAFTEE [77, 78] and will be compared for patients receiving ZNS or PLC using \Box^2 analysis or Fisher's exact tests, with an emphasis on moderate-to-severe adverse events.
- 6. K. 7. Sample Size And Power Estimate (Specific Aim 1): For continuous outcomes, based on the effect sizes from our pilot study of ZNS (showing a moderate effect size on drinks/week d=0.5, and .27 HDD/week), we estimated that a study with N=128 subjects (a 20% drop out rate) would be well powered (>.80) to detect a medium effect size difference on the secondary outcomes HDD per week and total drinks per week for the main effect of group assuming alpha level of 0.05. Based on past trials we are expecting a dropout rate < 30%. We will quantitatively examine the veteran and civilian populations for differences in variance and treatment response, and combine them (if valid) in a patient-level pooled analysis, further increasing power on all outcomes. If substantial differences are observed between the veteran and civilian samples, we will meta-analyze them. For PSNHDD, from the pilot study, in the ZNS group, 12 of 20 subjects did not relapse in the 28 days of the study, compared to 7 of 20 PLC subjects. Using this effect size, the proposed sample size of 80 subjects per group has >89% power to detect such a difference in the rates of no heavy drinking (i.e. 60% vs. 35%), assuming a two-sided alpha level of 0.05. We can also detect slightly smaller differences (60% vs. 38%, 35% vs. 57%) with 80% power under the same assumptions. Both in the estimation of effect

size from the pilot data and in the sample size analysis, dropouts are counted as relapsed to heavy drinking.

6 K. 8. Pharmacogenomic and Micro-longitudinal analyses power estimate (Aim 2, exploratory aims): There is little ZNS-specific data by which we could reasonably estimate effect sizes for these analyses. Three recent treatment studies by our group showed significant pharmacogenetic effects with samples of about 110-150 in each [15, 85, 102]. By using a mixed models approach on drinking variables, and HLM for the micro-longitudinal analyses, we will be adequately powered to detect medium-to-large effects in these analyses.

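### Choosing the primary model's covariance structure by BIC, with no candidate list and no robust standard error, can make the drinks-per-week test liberal if a serial-decay structure such as AR(1) wins

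*Combined protocol and SAP*

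**What the plan says.** Section 6.K.1.a makes drinks per week the primary outcome and analyses it with a mixed model: "The model will include fixed effects for medication group, week, and the interaction between medication and week". Baseline enters as one covariate: "We will include pre-treatment drinking behavior (past month HDD) as a covariate". For the covariance, the analysts "will select the best-fitting variance-covariance structure based on Schwartz-Bayesian Information criterion (BIC"). On timing, "we will focus the primary analysis on the last 8 weeks of treatment at the target dose".

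The same section defines success as a significant difference in "drinks per week, compared during the 8 weeks of active treatment at the target dose", and states that "The α will be set at .05 for the primary outcome variable". The power statement in Section 6.K.7 is "for the main effect of group assuming alpha level of 0.05".

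Section 6.K.2 repeats the BIC rule for heavy drinking days (HDD) per week, GGTP, AUQ and SIP, and applies Hommel's correction across the secondary outcomes.

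The text gives no list of candidate structures, ML or REML choice, degrees-of-freedom method, robust standard error, fallback structure or covariance sensitivity analysis. The one sensitivity analysis in Section 6.K.3, pattern-mixture models, addresses informative missingness and not the covariance.

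**The concern.** Success rests on one test at 0.05, and that test needs the right standard error for the group difference averaged over eight weeks. This standard error depends on the variance of a patient's 8-week mean, and so on the correlation between weeks far apart.

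Weekly drinking plausibly has two sources of correlation: a stable level for each person, and carry-over from one week to the next. AR(1) has one correlation parameter, set mainly by adjacent weeks, and it forces the correlation to decay towards zero with distance. If a stable person level is also present, AR(1) understates the long-lag correlation and therefore the variance of the mean.

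The one structure that is safe under any pattern, the unstructured matrix, is the one BIC penalises most. If a serial-decay structure is chosen and its model-based standard error is used, the primary test rejects too often under the null and its confidence interval is too narrow.

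**Working it through.** **Inputs from the documents.** 160 randomised 1:1; 128 evaluable after 20% dropout (64 per arm); an 8-week window, read as eight weekly values; alpha 0.05; d = 0.5 for drinks per week (6.B, 6.K.1.a, 6.K.7).

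**Assumptions.** The true correlations and the candidate structures are not in the documents. The test is taken as two-sided; 6.K.7 says "assuming a two-sided alpha level of 0.05" only for PSNHDD (the percentage with no heavy drinking days).

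**1. The plan's own figure.** With 64 per arm and d = 0.5, power is 0.807 by the normal approximation and 0.801 by the exact t-test. This reproduces the stated >0.80; sample size is not at issue.

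**2. The BIC penalty.** Eight weeks give an unstructured matrix 8 × 9 / 2 = 36 parameters, against 2 for compound symmetry (CS) or AR(1). The extra penalty for 34 parameters is 34 × ln(128) = 165, or 34 × ln(160) = 173.

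**3. One case by hand.** Assume unit variance made of a person component of 0.5 plus an AR(1) component of 0.5 with rho 0.6.
- The mean of the eight-week matrix of 0.6^lag is (8 + 2 × 8.313)/64 = 0.385. The true variance of a patient's 8-week mean is 0.5 + 0.5 × 0.385 = 0.692.
- The lag-1 correlation is 0.5 + 0.5 × 0.6 = 0.8, so the best-fitting AR(1) has rho 0.8. The mean of the matrix of 0.8^lag is (8 + 2 × 15.355)/64 = 0.605.
- The SE ratio is √(0.605/0.692) = 0.935. The implied type I error is 2[1 − Φ(1.96 × 0.935)] = 0.067.
- CS fits the average off-diagonal correlation, (64 × 0.692 − 8)/56 = 0.648. It gives (1 + 7 × 0.648)/8 = 0.692, exactly the true value.
- Fit is compared by the log-determinant per patient. AR(1): 7 ln(1 − 0.64) = −7.15. CS: 7 ln(0.352) + ln(5.539) = −5.61. Truth: 8 ln 0.5 + 7 ln 0.64 + ln 3.75 = −7.35.
- At N=128, AR(1) beats CS by about 1.55 × 128 = 198. The unstructured form improves on AR(1) by only about 0.196 × 128 = 25, plus roughly 34 for chance fit, far below its penalty of 165. BIC picks AR(1).

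**4. Null simulation.** Candidates CS, AR(1) and unstructured; complete data; 8000 replicates per setting (Monte Carlo error 0.002 to 0.003).

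| Assumed truth | BIC, 80/arm | BIC, 64/arm | Unstructured |
|---|---|---|---|
| CS, 0.6 | 0.048 | 0.049 | 0.048, 0.049 |
| AR(1), 0.8 | 0.045 | 0.049 | 0.047, 0.048 |
| Person 0.5 + AR(1) 0.5, rho 0.6 | 0.064 | 0.067 | 0.049, 0.049 |
| Person 0.4 + AR(1) 0.3, rho 0.7 + noise 0.3 | 0.050 | 0.054 | 0.047, 0.051 |
| Person 0.1 + AR(1) 0.4, rho 0.7 + noise 0.5 | 0.072 | 0.073 | 0.047, 0.049 |

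BIC never chose the unstructured form. The third row matches the hand calculation. With 20% random dropout (600 replicates, 80 per arm), that row gave 0.062 under BIC and 0.048 unstructured.

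**5. Range.** Further person-plus-AR(1) covariances at 64 per arm (4000 trials each) gave SE ratios of 0.89 to 0.98 and type I errors of 0.054 to 0.082, against 0.045 to 0.055 unstructured. Over a grid of 192 structures the median SE ratio was 1.00, and 36% of structures fell below 0.98.

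**6. Wider candidate lists.** With Toeplitz added, one covariance gave 0.054 (500 trials). With random intercept plus AR(1) added, six covariances gave 0.049 to 0.060 and SE ratios of 0.99 to 1.00 (1000 trials each). With unequal weekly variances, BIC chose ARH(1) from a wider list and the ratio stayed at 0.94 (200 replicates).

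**7. Secondary outcomes.** Weeks 9 to 16 hold eight weekly HDD values. They hold four AUQ values (weeks 9, 11, 13 and 16) and one SIP value (week 16) by Table 2, and two GGTP values (weeks 9 and 16) by Section 6.G.1.

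**The case against.** The strongest reply is that the inflation comes from an unduly short candidate list. The plan calls its method a mixed model, and a patient-level random intercept is the basic element of one. Once random intercept plus AR(1) or Toeplitz is available, BIC usually finds it and the type I error returns close to 0.05. BIC is also an objective rule stated in advance: it compares covariance fit and does not look at the treatment effect. Much of this stands. It does not close the point, because the plan does not say those structures will be tried, and ARH(1) could still win with too small a standard error when weekly variances differ.

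A reader might infer four stronger claims, none of which the documents support:
- **That any simple structure makes the standard error too small.** CS is as simple as AR(1) and, with complete data, gives the correct standard error for the 8-week mean. AR(1) does not always win either: with person 0.5, AR(1) 0.5 and noise 0.1, one run chose it in 76% of trials and CS in 24%.
- **That the type I error is about 0.10.** That is a large-sample extreme on the grid (SE ratio 0.836). Simulated at trial size, the same structure gave 0.072 to 0.073, because CS won in nearly half the trials.
- **That the structure is picked on unblinded data.** The plan does not say when or by whom the selection is made.
- **That every continuous secondary outcome is affected alike.** The eight-week argument fits HDD per week. It does not carry over to GGTP, SIP or AUQ, which have two, one and four values in the window.

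**Conclusion.** The point holds in conditional form. The stated rule will in practice exclude the unstructured matrix, and nothing else in the plan protects the standard error. If a serial-decay structure wins while patients differ persistently, the standard error of the 8-week group difference is about 2% to 11% too small in the covariances examined. The type I error is then about 0.05 to 0.08 against a nominal 0.05. If CS wins with complete data there is no inflation, and with a suitable candidate list and equal weekly variances there is little.

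These figures rest on assumed correlations, normally distributed data and a test of the group difference averaged over eight weeks. The simulations omitted the past-month HDD covariate, which may absorb part of the person-level component, and did not examine group-by-week tests. The size for this trial cannot be determined from the documents. This is a cheap improvement to the primary analysis, not an arithmetic error.

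**What to change.** In Sections 6.K.1.a and 6.K.2, for drinks per week and HDD per week over weeks 9 to 16, replace the BIC selection with a pre-specified unstructured covariance and Kenward-Roger degrees of freedom. Name the fallback if it does not converge: Toeplitz with sandwich standard errors.

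If the team prefers to keep BIC, list the candidates in advance, include Toeplitz and random intercept plus AR(1), and report sandwich standard errors whichever structure is chosen.

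The cost is about one sentence, a few degrees of freedom (under about one point of power) and a possible convergence failure, which the fallback covers. With complete data the estimated 8-week difference is the same under every structure, so the sample size need not change. In the checks above, the pre-specified unstructured form held the type I error at 0.047 to 0.051 with complete data (8000 replicates) and 0.043 to 0.048 with 20% dropout (600 replicates).

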Specific Aim 1) To evaluate fully the efficacy of and scope of effectiveness for ZNS in treating AUDs by adding a civilian arm (*N*=160 randomized, 80 on ZNS and 80 on placebo) to the CSR&D-funded study in veterans, using the same primary outcome (drinks per week) and secondary measures of drinking behavior as the veteran arm [i.e., heavy drinking days/week, percentage of subjects with no heavy drinking days (PSNHDD), craving, reductions in GGT]. Subjects will meet criteria for an AUD (DSM-5) and be heavy drinkers similar to the participants in the VA study. We hypothesize that ZNS will produce a significantly greater reduction in drinks per week than placebo (primary outcome alpha = .05). We also hypothesize that ZNS will significantly improve secondary measures of drinking (corrected for multiple comparisons). We will recruit civilians from the University of Connecticut Health Center (UCHC) and VCU's Institute for Drug and Alcohol Studies (IDAS)

Specific Aim 2) To use telephone-based daily process data collection to elucidate the mechanism of action of ZNS as it relates to changes in craving, anxiety, and genetic variation. This method has been shown to elucidate the mechanism of action of topiramate, as well as its pharmacogenetic interactions. We hypothesize that ZNS' effects will be moderated by genetic variation, craving, and anxiety, but mediated through changes in self-efficacy to reduce heavy drinking.

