Exclusion criteria are: a) a current, clinically significant physical disease [i.e., neurologic, renal, rheumatologic, gastrointestinal, hematologic, pulmonary, endocrine, cardiovascular, hepatic, or autoimmune disease] on the basis of medical history, physical examination, or routine laboratory evaluation that, in the context of the study would represent a risk to the subject, or significant laboratory abnormalities related to hepatic function such as marked elevations of hepatic aminotransferase levels (i.e., AST and ALT) or direct bilirubin. Other specific exclusionary disorders include; b) history of clinically significant renal calculi or renal failure: renal compromise (defined by an elevation of serum creatinine above our laboratory's limit of normal);c) history of hypersensitivity to ZNS, or any sulfonamide, Stevens-Johnson Syndrome, or history of any severe drug allergic reaction; d) current clinically significant blood dyscrasia, e) history of seizure disorder; f) use of any of a number of medications that might prominently influence drinking patterns or cause risk of harm or injury (e.g., FDA approved medications to treat AUD, chronic use of opioid pain medication or benzodiazepines, tramadol); g) schizophrenia, bipolar disorder, or substantial suicide or violence risk on the basis of history or psychiatric examination; h) currently dependent on opioids or benzodiazepines; i) are considered to be unsuitable candidates for receipt of an investigational drug; j) patients who report having 5 or more standard drinks within 24 hours of urine ETG sample collection at screening will be excluded if their ETG levels are negative.

6.D.Temporal Sequence of Study Procedures: Following telephone screening to determine initial eligibility, patients will be invited to the clinical site for an in-person visit. At the first inperson visit, informed consent will be obtained and patients will undergo a screening interview

to assess inclusion and exclusion criteria. Patients excluded at any point in the recruitment process will be referred for appropriate treatment based upon consultation with the study physician (See Section 6.I "Other Treatments Allowed During the Study" for a more detailed explanation). If subjects are unable to complete the entire screening procedures in 1 visit due to their schedule, they may be allowed to return for additional visits if needed prior to baseline.

6.E. Schedule of Visits:

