6.G. Assessments: We include measures from different sources (see **Table 2**) to cover the various domains in which alcohol treatment may exert an effect and to corroborate self-reported treatment effects.

Study data will be collected and managed using REDCap electronic data capture tools hosted at VCU. REDCap (Research Electronic Data Capture) is a secure, web-based application designed to support data capture for research studies, providing 1) an intuitive interface for validated data entry; 2) audit trails for tracking data manipulation and export procedures; 3) automated export procedures for seamless data downloads to common statistical packages; and 4) procedures for importing data from external sources [52].

- **6.G.1.** Laboratory/Medical Assessments: These assessments serve to: 1) screen patients for medical exclusion criteria, 2) assess potential adverse effects of ZNS, and 3) corroborate self-reported drinking. Prior to entrance into the study, each patient will receive a physical exam, urinalysis and urine toxicology, CBC, a chemistry panel [which includes electrolytes, liver enzymes (ASAT, ALAT, GGTP), bilirubin, uric acid, BUN, and creatinine], and pregnancy testing. Bicarbonate levels will be every 4 weeks because ZNS can cause metabolic acidosis; pregnancy testing and a CBC will also be repeated at the midpoint, which is planned to be week 9 but may be adjusted per patient visit needs. If a patient reports being pregnant or tests positive, she will immediately be excluded or withdrawn from treatment with medication, referred for obstetric evaluation, and advised to discontinue all drinking. At the midpoint (week 9) and endpoint (week 16), GGTP will be repeated to corroborate self-reported alcohol consumption. The patient will be in the downward titration phase of the medication at this point (See Table 1: Medication Titration Schedule). We will also obtain Ethyl Glucuronide (EtG), Ethyl Sulfate (EtS), and Phosphatidyl Ethanol (PEth) as biomarkers to verify subjective claims of drinking during the study.
- **6.G.2. Psychological/Behavioral Assessments:** ZNS is hypothesized to have its greatest influence on alcohol consumption. The assessments listed below measure multiple outcome criteria, because a reduction in drinking may not result in improvement in other domains.

Table 2: Schedule of Assessments

Table 2: Sch				Study Week								
	SC	BL	1	3	5	7	9	11	13	16	18	28
Surveys/Procedures												
Overview and Consent	Х											

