6.K.2 Secondary outcome measures: We will use a mixed models approach to examine for a statistically significant difference on heavy drinking days (HDD) per week, changes in GGTP level, measures of alcohol urge/craving (AUQ), and alcohol-related problems (as measured on the SIP). For each of these outcome measures, the model will include fixed effects for medication group, week, and the interaction between medication and week. We will include pre-treatment drinking behavior (past month HDD) as a covariate and will select the best-fitting variance-covariance structure based on Schwartz-Bayesian Information criterion (BIC). We will incorporate a grace period corresponding to the time it takes to titrate the medication to target dose into the models, and we will focus the primary analysis on the 8 weeks of treatment at the target dose. We will use the Hommel's correction for multiple comparisons on the secondary outcomes to guard against chance findings. With last secondary outcome measure percentage of subjects with no heavy drinking days (PSNHDD), we will use a logistic regression analysis with PSNHDD as a categorical dependent variable. Medication condition (PLC or ZNS) will be the main independent variable, and we will include the variables of civilian or veteran status. and sex as covariates. We will also examine the use of biomarkers (GGT, PEth) to verify and adjust subjective drinking data as these biomarkers can detect occult harmful drinking when a subject is not forthcoming.

6. K. 3. Dropouts and missing data: For the analysis of PSNHDD using logistic regression, all dropouts will be counted as relapsed. For all repeated measures analysis, we will use all V.6 05Jun2020

available data on individuals and thus dropouts provide data until the point of dropout. We will compare dropout patterns between groups and if there are concerns of informative dropout and/or informative intermittent missing data, we will use pattern mixture models [98] to perform sensitivity analyses to our main analyses. Adherence to the medication will be evaluated and controlled for in secondary analyses. We will evaluate and compare both medication conditions (PLC, ZNS) for percentage of prescribed pills taken.

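### Section 6.K.2 names no analysis scale for change in GGTP and leaves out baseline GGTP; read as written (untransformed change), it loses power if GGTP is right-skewed

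*Combined protocol and SAP*

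**What the plan says.** Specific Aim 1 names "reductions in GGT" among the secondary measures. Section 6.K.2 carries this into the analysis as "changes in GGTP level" and gives it the same model as the other continuous secondaries: "the model will include fixed effects for medication group, week, and the interaction between medication and week". The baseline term is set by "We will include pre-treatment drinking behavior (past month HDD) as a covariate". Multiplicity is handled by "We will use the Hommel's correction for multiple comparisons on the secondary outcomes to guard against chance findings"; five secondaries are listed there (heavy drinking days per week, GGTP, AUQ, SIP, and the percentage with no heavy drinking days).

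GGTP is measured at screening (6.E.1) and then on treatment: "At the midpoint (week 9) and endpoint (week 16), GGTP will be repeated to corroborate self-reported alcohol consumption" (6.G.1).

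For GGTP the plan names no transformation, residual check, or robust or rank method. Baseline GGTP is not listed as a covariate. Section 6.K.4 does deal with distribution for the nighttime drink counts, with a Poisson or negative binomial model. The hepatic exclusion in 6.C gives "marked elevations of hepatic aminotransferase levels" and direct bilirubin as examples and sets no numerical limit on GGTP.

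**The concern.** A serum enzyme level is positive and may have a long upper tail, and a treatment effect on it may act more nearly as a proportion than as a fixed number of units. If so, the patients with the highest baselines also have the largest absolute changes. On the raw scale they set the residual variance, and a real proportional fall in the rest of the sample is harder to detect. Omitting baseline GGTP adds to this, because the change score then keeps variation that the baseline value would explain.

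At stake is the power of one of five corrected secondary tests. GGTP is also one of the biological measures placed beside self-reported drinking, so a between-arm difference missed through choice of scale would remove one piece of supporting evidence.

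**Working it through.** **Inputs from the plan.** Evaluable sample 128 after 20% dropout from 160 (6.K.7): 160 × 0.80 = 128, or 64 per arm. Alpha 0.05, taken as two-sided. No GGTP mean, SD, range or effect size is given.

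**Inputs assumed.** Log-normal GGTP; SD of log GGTP (s) 0.5 to 1.0; pre-post correlation (r) 0.6 or 0.8; true fall of 20% or 30% on zonisamide relative to placebo; no common change in both arms; one post-baseline time point.

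**1. The plan's own figure.** For d = 0.5 and 64 per arm, 0.5 × √(64/2) = 2.83 and Φ(2.83 − 1.96) = 0.807 (exact t-test 0.801). The stated power above 0.80 for continuous outcomes reproduces. It is not specific to GGTP.

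**2. Log change, closed form.** SD of log change = s × √(2(1 − r)), and d = −ln(1 − fall) / SD. For s = 0.6, r = 0.8 and a 20% fall: SD = 0.6 × √0.4 = 0.379; d = 0.223 / 0.379 = 0.588; 0.588 × √32 = 3.33; Φ(3.33 − 1.96) ≈ 0.91.

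**3. Raw against log, simulated.** 10,000 trials per row. Change is compared by two-sample t-test; the last two columns use the GGTP value with its own baseline as covariate.

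| Fall | r | s | Raw change | Log change | Raw + baseline | Log + log baseline |
|---|---|---|---|---|---|---|
| 20% | 0.8 | 0.5 | 0.91 | 0.98 | 0.97 | 0.99 |
| 20% | 0.8 | 0.6 | 0.75 | 0.91 | 0.85 | 0.93 |
| 20% | 0.8 | 0.8 | 0.44 | 0.69 | 0.54 | 0.73 |
| 20% | 0.8 | 1.0 | 0.25 | 0.51 | 0.32 | 0.55 |
| 20% | 0.6 | 0.5 | 0.66 | 0.80 | 0.82 | 0.87 |
| 20% | 0.6 | 1.0 | 0.16 | 0.30 | 0.21 | 0.35 |
| 30% | 0.8 | 0.5 | 1.00 | 1.00 | 1.00 | 1.00 |
| 30% | 0.8 | 0.6 | 0.97 | 1.00 | 1.00 | 1.00 |
| 30% | 0.8 | 0.8 | 0.78 | 0.98 | 0.90 | 0.99 |
| 30% | 0.8 | 1.0 | 0.49 | 0.89 | 0.65 | 0.91 |
| 30% | 0.6 | 1.0 | 0.31 | 0.62 | 0.47 | 0.72 |

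The smallest loss for raw change against log change is about 0 points (30% fall, r = 0.8, s = 0.5). The largest is about 37 to 39 points across separate runs (30% fall, r = 0.8, s = 1.0).

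**4. How much is baseline and how much is scale.** For a 20% fall, r = 0.8 and s = 0.6, adding baseline GGTP without a log moves power from 0.75 to 0.85, which is 10 of the 16 points between raw and log change. At s = 1.0 it moves from 0.25 to 0.32, 7 of 26 points. Baseline adjustment explains much of the gap under mild skew and less under strong skew.

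**5. Mechanism.** In a separate run with a common fall of about 10% in both arms, the 6 most extreme of 128 patients carried 32% (s = 0.3) to 73% (s = 1.2) of the sum of squares of raw change, against 26% on the log scale. Type I error across all methods was 0.040 to 0.054, so the cost is in power only.

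**6. If eligibility trims the tail.** With the top 10% of baselines removed (20% fall, r = 0.8), raw against log change is 0.85 against 0.91 (s = 0.6), 0.58 against 0.70 (s = 0.8) and 0.35 against 0.51 (s = 1.0).

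**7. Under Hommel.** The strictest level with five tests is 0.05 / 5 = 0.01. With the effect set so that log change has about 80% power at 0.05, power at 0.01 is 57% to 58% for log change and 10% to 44% for raw change (s from 0.3 to 1.2).

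**The case against.** The strongest reply is that the raw scale is inferred from silence. Section 6.K.2 names the outcome and a mixed-model approach; it never says untransformed or normal, and 6.K.4 uses mixed models for count data too. This stands to the extent that a reader should not infer that the plan commits itself to the raw scale. It does not dispose of the point: no alternative is named, so the text read as written gives an untransformed change, and a scale chosen after the data are seen would be worse.

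A reader might also infer that patients with very high GGTP are bound to be enrolled. The documents do not support that. The hepatic exclusion covers clinically significant hepatic disease, its laboratory abnormalities are given only as examples, and 6.G.1 lists GGTP among the screening liver enzymes, so some high values may be excluded by judgement. Step 6 shows that trimming shrinks the loss but does not remove it.

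Three further replies hold. The skew and the proportional effect come from outside the documents, and some plausible settings give almost no loss. Part of the loss belongs to the missing baseline covariate. The simulations use one time point at unadjusted 0.05, whereas the plan has repeated measures, Hommel's correction and possible pooling with the veteran sample.

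Finally, a reader might infer that the primary result is weakened. Success is defined on drinks per week alone (6.K.1.a), self-report is also checked with PEth, EtG and EtS, and checking an individual's report against GGTP does not depend on the scale of the between-arm test.

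**Conclusion.** The point holds as a minor one. The GGTP scale is not pre-specified, baseline GGTP is omitted, and the analysis as written reads as untransformed change. If GGTP is right-skewed, that costs power, from nothing to about 37 to 39 points over the assumed range, with no inflation of type I error. Log change equalled or beat raw change in every setting run. The size rests on log-normality, a proportional effect and assumed SDs and correlations, none of which the documents supply; it is smaller with mild skew, a trimmed tail or adjustment for baseline. The point concerns one secondary outcome and leaves the primary analysis and the sample size as they are.

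**What to change.** Add to 6.K.2, before unblinding: *GGTP at weeks 9 and 16 is analysed as log(GGTP) with log baseline (screening) GGTP as a covariate; the treatment effect is reported as a ratio of geometric means, with raw medians by arm shown descriptively.* The baseline term matters as much as the log, since under mild skew it recovers a large share of the loss.

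The cost is one sentence, with no new data collection. The effect is expressed as a percentage difference, not in enzyme units; the descriptive medians partly offset this. If skew turns out to be mild, little is lost by the change.
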